## 15 Appendix 3: Specific Renal Alert Criteria and Actions

**Table 15-1 Specific Renal Alert Criteria and Actions**

| Serum Event  |   |
|---|---|
| Serum creatinine increase
25 – 49% compared to baseline  | Confirm 25% increase after 24-48h
Follow up within 2-5 days  |
| Acute Kidney Injury: Serum creatinine increase $\geq$
50% compared to baseline   | Follow up within 24-48h if possible
Consider study treatment interruption
Consider patient hospitalization /specialized treatment |
| Urine Event  |   |
| New dipstick proteinuria $\geq$ 1+
Albumin- or Protein-creatinine ratio increase $\geq$ 2-fold
Albumin-creatinine ratio (ACR) $\geq$ 30 mg/g or
$\geq$ 3 mg/mmol;
Protein-creatinine ratio (PCR) $\geq$ 150 mg/g
or $>$ 15 mg/mmol   | Confirm value after 24-48h
Perform urine microscopy
Consider study treatment interruption / or
discontinuation                 |
| New dipstick glycosuria $\geq$ 1+ not due to diabetes   | Blood glucose (fasting)
Perform serum creatinine, ACR  |
| New dipstick hematuria $\geq$ 1+ not due to trauma  | Urine sediment microscopy
Perform serum creatinine, ACR  |
| For all renal events:  |   |
| Document contributing factors in the CRF: co-medication, other co-morbid conditions, and additional diagnostic procedures performed
Monitor patient regularly (frequency at investigator's discretion) until either:
Event resolution: sCr within 10% of baseline or protein-creatinine ratio within 50% of baseline, or
Event stabilization: sCr level with $\pm$ 10% variability over last 6 months or protein-creatinine ratio stabilization at a new level with $\pm$ 50% variability over last 6 months. |   |

This document contains details of the statistical methods which will be used in the phase IV post-marketing clinical trial CENA713DJP02. The statistical analysis described in this SAP is based on the final study protocol and will be presented in the Clinical Study Report. This is a 24-week, open-label, multicenter study to evaluate the efficacy, safety and tolerability of Exelon patch (Rivastigmine) with 1-step titration in patients with mild to moderate Alzheimer's disease (MMSE 10 – 23) switched directly from cholinesterase inhibitors (donepezil, galantamine) in Japan.

1.1 Overall study design

This study will have three phases:

Screening phase [2-4 weeks: week -4 (Day -28) to week -2 (Day -14 to Day -1)].

The Screening Visit (Visit 1) has to take place 2 – 4 weeks before the planned start of rivastigmine patch treatment. After signing the informed consent, all patients will undergo a preliminary evaluation (Screening Visit) to assess eligibility ([Appendix 16.1.1-Protocol-Section 4.1](#)). Patients will continue their ChE inhibitors (donepezil or galantamine) during the Screening period, and patients are eligible to take their ChE inhibitors until the evening prior to start day of rivastigmine patch. For those patients who are eligible to enroll the study by the preliminary evaluation at Screening Visit, MMSE score during previous 6 months should be collected and recorded as much as possible. Their ChE inhibitors are discontinued on Baseline visit (Day 1). At the baseline visit (Visit 2), the patient will also undergo safety and efficacy assessments as per [Appendix 16.1.1-Protocol-Table 6-1](#), and eligibility will be confirmed. Day 1 will be the day on which treatment with rivastigmine patch will be started. Patients will be starting on treatment with rivastigmine patch on the same day of the baseline visit (Day 1). When the patients already took their ChE inhibitors at the baseline visit (Visit 2, Day -1), the patients will start on treatment with rivastigmine patch the next day (Day 1) after the baseline visit.

Titration phase [8 weeks: week 1 (Day 1) to week 8 (Day 56)].

[figure not shown]
On the same day or next day (Day 1) following baseline visit, patients will begin treatment with a rivastigmine patch 9.0 mg/day and will be up-titrated after 4 weeks to reach the maintenance dose of 18 mg/day. Should tolerability problems occur, the investigators can decide to interrupt the treatment temporarily or to reduce the dose (see [Appendix 16.1.1-Protocol-Section 5.5.5](#)). The highest well-tolerated dose for each individual patient should be established within the titration period. The investigators also can use their clinical judgement to switch those patients to slower 3-step titration scheme in order to reach the maintenance dose of 18 mg/day or find the highest well-tolerated dose for each individual patient. Those patients will be allowed to stay in the study. During the titration period, visits will take place every 4 weeks.

Maintenance phase [16 weeks: week 9 (Day 57) to week 24 (Day 168)].

The patients will be maintained on the maintenance dose of rivastigmine patch 18 mg/day (or highest well-tolerated dose) during the remaining period of the study and will undergo safety and efficacy assessments as per protocol. If 18 mg/day is not achieved at maintenance period,

it will be increased up to 18 mg/day if possible. Patients not tolerating the 18 mg/day will stay on their highest tolerated dose in the study and will undergo safety and efficacy assessment as per protocol.

Figure 1-1 **Study design**

The planned number of patients to be enrolled in the study is 97. There are no planned interim analyses.

1.2 Study objectives and endpoints

Objectives	Endpoint Title, Description and Reporting Time Frame for analysis and Unit of Measure	Protocol Statistical Analysis Section
Primary		
To evaluate the efficacy of rivastigmine patch with 1-step titration on cognitive function measured as change from baseline to week 24 in the total score of MMSE in mild to moderate AD patients who failed to benefit from other cholinesterase inhibitors (ChEIs)	Endpoint Title: Change from baseline to week 24 in the total score of MMSE Time Frame : Up to week 24	Appendix 16.1.1-Protocol-Section 9.4
Secondary		
To evaluate the safety, tolerability of Exelon® patch with 1-step titration for up to 24 weeks.	Endpoint Title: Monitoring and recording of all adverse events (AEs) and serious adverse events (SAEs). Time Frame: Up to week 24.	Appendix 16.1.1-Protocol-Section 9.5

Objectives	Endpoint Title, Description and Reporting Time Frame for analysis and Unit of Measure	Protocol Statistical Analysis Section
To evaluate the efficacy of Exelon® patch with 1-step titration measured as the MMSE score at week 8.	Endpoint Title: Change from baseline to Week 8 in MMSE total score. Time Frame : Week 8	
To evaluate the efficacy of Exelon® patch with 1-step titration measured as the NPI-10 score at week 8 and week 24.	Endpoint Title: Change in NPI-10 score from baseline to week 8 and week 24 Time Frame : Week 8 and Week 24	
To evaluate the efficacy of Exelon® patch with 1-step titration measured as QOL-AD score at week 24.	Endpoint Title: Change in QOL-AD score from baseline to week 24 Time Frame : Week 24	Appendix 16.1.1-Protocol-Section 9.5
To evaluate the efficacy of Exelon® patch with 1-step titration measured as the J-CGIC score at week 4, week 8, week 16, and week 24.	Endpoint Title: Change in J-CGIC score from baseline to week 4, 8, 16 and 24 Time Frame : Week 4, 8, 16, 24	
To evaluate the efficacy of Exelon® patch with 1-step titration measured as Modified Crichton Scale score week 4, week 8, week 16, and week 24.	Endpoint Title: Change in as Modified Crichton Scale score from baseline to week 4, 8, 16 and 24 Time Frame : Week 4, 8, 16, 24	
To evaluate the formulation usability of Exelon® patch for up to 24 weeks as measured by the formulation usability questionnaire answered by caregiver.	Endpoint Title: Formulation usability score up to week 24 Time Frame : Up to week 24	

2 Statistical methods

This section contains information that will be used to draft CSR Section 9.7 on statistical analysis.

2.1 Data analysis general information

All data will be analyzed by Novartis using the statistical software SAS version 9.4 according to the data analysis section 9 of the study protocol which is available in Appendix 16.1.1 of the CSR. Important information is given in the following sections and details are provided, as applicable, in Appendix 16.1.9 of the CSR.

In general, the continuous variables will be summarized using standard descriptive statistics (mean, median, standard deviation, first (Q25) and third (Q75) quartile, minimum and maximum) and the categorical variables will be summarized in terms of the number and percentage of patients in each category.

2.1.1 General definitions

2.1.1.1 Study treatment

In this study aims to evaluate the tolerability, safety and efficacy of rivastigmine patch with 1-step titration in applicable patients with mild to moderate AD switched directly from cholinesterase inhibitors (donepezil, galantamine). Therefore, for these patients who had 1-step titration, study treatments are:

Form	Size
Exelon® patch 9 mg	5 cm ²
Exelon® patch 18 mg	10 cm ²

However, for patients who cannot tolerate 1-step titration method to reach the maintenance patch dose of 18 mg/day, the investigators will use their clinical judgement to switch those patients to slower 3-step titration method in order to reach the maintenance dose of 18 mg/day or find the highest well-tolerated dose for each individual patient. Once the dose started at 4.5 mg of rivastigmine once a day, as a general rule, the dose should be increased to 4.5 mg a day at 4-week intervals to 18 mg once a day. Therefore for these patients, study treatments are:

Form	Size
Exelon® patch 4.5 mg	2.5 cm ²
Exelon® patch 9 mg	5 cm ²
Exelon® patch 13.5 mg	7.5 cm ²
Exelon® patch 18 mg	10 cm ²

Patients who cannot tolerate 1-step titration will be allowed to participate in the study but will be excluded from the per protocol analysis only.

No control treatment is planned in this study.

2.1.1.2 Study day

Study day is defined with respect to the first day on which treatment with rivastigmine patch starts. The date of first administration of study medication is defined as Day 1 and the day before is defined as Day -1. There is no Day 0 in a study.

Therefore, for any particular date, study day will be calculated as follows:

- for dates on or after the first date of study medication administration,
Study day = Assessment date – Date of first administration of study medication + 1;
- for dates prior to the first date of study medication administration,
Study day = Assessment date – Date of first administration of study medication.

2.1.1.3 Baseline definition

Baseline visit (typically Visit 2) is defined as the day on which patients discontinue their prior ChE inhibitors. The baseline visit (Visit 2) may or may not be the same as Day 1. .

- It will be same as Day 1 if the patients already stop their ChE inhibitors prior to Day 1 and starts treatment with revastigmine patch from Day 1.
- on the otherhand, baseline visit (Visit 2, Day -1) will be one day before the Day 1 start of study treatment if the patients already took their ChE inhibitors at Visit 2.

In general, all assessments taken prior to the start of study treatment at Visit 2 will be considered as the baseline assessment. However, if the baseline assessments for MMSE, vital signs and laboratory parameters at Visit 2 are missing, then the measurements taken at Visit 1 (if available, as per protocol assessment schedule Table 6-1) will be used as baseline.

2.1.1.4 Post-baseline assessments

Post-baseline values are defined as assessments taken after the start of study treatment.

When change from baseline is of interest the following formula will be used for each scheduled visit and time-point where baseline and post-baseline values are both available: **Change from baseline = post-baseline value – baseline value.**

2.2 Analysis sets

Full Analysis Set (FAS)

The FAS will include all patients who received at least one dose of study treatment and had at least a baseline and any post-baseline assessment on treatment. This is the primary analysis population and will also be used for all efficacy analyses.

Per protocol Set (PP set)

The per protocol set will include all patients in the FAS who had only 1 step titration without any major deviations from the protocol procedures. The major protocol deviations will be specified prior to database lock.

Safety Set (SAF)

The safety set will consist of all patients who received at least one dose of drug and had at least one post-baseline safety assessment.

2.2.1 Subgroup of interest

2.2.1.1 Subgroup analyses for efficacy endpoints

The following subgroup analyses will be performed for the change from baseline in the total MMSE score at each post-baseline visit (i.e., Week 8 and Week 24):

- age (\leq 60 years, $>$ 60 years)*
- weight (\leq median, $>$ median, in kg, to be determined from the data)
- MMSE at baseline (10-14, 15-23 and further 15-23 into 15-19 and 20-23)*
- treatment regimen (e.g., overall, 1-step and 3-step titration)
- reason for switching to 3-step titration (as captured in the DAR page of CRF, e.g., adverse events, lab or test abnormality, lack of efficacy)
- Overall compliance to study medication (<75% and 75-100%)
- Patient profile analysis 1a: Use of skin moisturizer at baseline (yes/no)*
 - ◆ Total
 - ◆ Compliance to study medication (<75% and 75-100%)

Note: skin moisturizer will be identified using the data captured in the prior and concomitant medication CRF page and confirmed by the clinical team.

- Patient profile analysis 1b: Use of skin management at least one time during study period (yes/no)*
 - ◆ Total
 - ◆ Compliance to study medication (<75% and 75-100%)

Note: skin management will be identified using the data captured in the prior and concomitant medication CRF page and confirmed by the clinical team.

- Patients satisfying protocol inclusion criteria 9-1 only, 9-2 only and both, respectively captured in the CRF page, are specified below:*

- ◆ Inclusion criteria 9-1: Patients who are not responding to the previous treatment can be defined if the patients meet at least one of these conditions at baseline:
 - Patients who declined \geq 2 points of MMSE despite of treatment of other oral ChE inhibitors within initial 3-month and continued to show insufficient treatment effect until at baseline.
 - During 6 months prior to screening visit, Patients who declined \geq 2 points of MMSE with other oral ChE inhibitors and continued to show insufficient treatment effect until at baseline.
 - Patients who show marked worsening of BPSD, or ADL (can be defined by 1 state progression of FAST) judged by a physician despite

of treatment of other oral ChE inhibitors in initial 3-month or last 6-month with other oral ChE inhibitors

- ◆ Inclusion criteria 9-2: Patients having difficulties being treated orally with ChEIs (donepezil or galantamine) by physician's judgement. Difficulties are defined if the patients meet at least one of these conditions at baseline:*
- Inadequate compliance with the ChE inhibitors at screening and baseline
- Inadequate treatment (efficacious dose was not reached or inadequate compliance) with the ChE inhibitors because of AEs except gastrointestinal (GI) symptoms (nausea and vomiting) at screening and baseline
- Patients with swallowing difficulties at screening and baseline

Further, a subgroup analysis will be presented for patients satisfying inclusion criteria

- 9-1 only, 9-2 only and both 9-1 and 9-2
- 9-1-1 only, 9-1-2 only, 9-1-3 only, and 9-1-1 and 9-1-3, and 9-1-2 and 9-1-3
- (9-1-1 or 9-1-2) versus (9-1-2 and 9-1-3) versus 9-1-3 only
- 9-1 versus 9-2
- (9-1 only) versus (9-1 and 9-2) or (9-2 only)
- (9-2 only) versus (9-1 and 9-2) or (9-1 only)

- Patients with concomitant use of memantine (yes/no)
- Patients satisfying treatment retention criteria as in Section 2.9.1 (yes/no)

Note: * items will also be illustrated using figures for the CSR.

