#### **4.1 Inclusion criteria**

Patients/subjects eligible for inclusion in this study must fulfill all of the following criteria:

1. Written informed consent of the patient and legal representative will be obtained before any assessment is performed (MUST be signed by the legal representative if a signed informed consent from patients is difficult, consent can only be obtained from the patients orally) at Screening.
2. Patients within the age of 50-85 years at Baseline.
3. Outpatient status at Baseline.
4. Males and females not of child-bearing potential.
  - Women are considered post-menopausal and not of child bearing potential if they have had 12 months of natural (spontaneous) amenorrhea with an appropriate clinical profile (e.g. age appropriate, history of vasomotor symptoms) or have had surgical bilateral oophorectomy (with/without hysterectomy) or tubal ligation at least six weeks previously.
5. A diagnosis of dementia of the Alzheimer's type according to the DSM-IV criteria.
6. A clinical diagnosis of probable AD according to National Institute of Neurological and Communicative Disorders and Stroke - Alzheimer's Disease and Related Disorders Association (NINCDS-ADRDA) criteria and meeting any of following criteria.
  - Brain scan (magnetic resonance imaging [MRI], or computed tomography [CT]) were met diagnosis criteria conducted within 3 years prior to baseline (Imaging within 1 year prior to baseline is preferable).
  - Positron emission tomography (PET) or single photon emission computed tomography (SPECT) was met diagnosis criteria conducted within 3 years prior to baseline visit; as long as in the past a brain scan (MRI or CT) was also met (Imaging within 1 year prior to baseline is preferable).
7. An MMSE score of  $\geq 10$  and  $\leq 23$  at screening and baseline.
8. Patients are currently on the oral monotherapy (donepezil, 5 mg), or galantamine (16-24 mg) for 4 weeks prior to baseline visit.
9. Patients who could not receive treatment benefits of previous oral ChEIs can be defined by meeting the following criteria, either 9-1, 9-2, or both.
  - 9-1. Patients who are not responding to the previous treatment can be defined if the patients meet at least one of these conditions at screening and baseline
    - Patients who declined  $\geq 2$  points of MMSE despite of treatment of other oral ChE inhibitors within initial 3-month and continued to show insufficient treatment effect until at baseline.

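### SAP 2.2.1.1: in the three-way row on criterion 9-1 the second group lies inside the first, so the subgroup model cannot be fitted to the row as worded

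*SAP*

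**What the plan says.** Protocol 4.1, point 9, admits patients by "meeting the following criteria, either 9-1, 9-2, or both". Point 9-1 has three conditions and counts a patient as not responding "if the patients meet at least one of these conditions at screening and baseline". The Protocol summary adds that more than one may be chosen. Overlap between conditions, and between 9-1 and 9-2, is thus expected.

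SAP 2.2.1.1 plans subgroup analyses of the change in MMSE total score at Weeks 8 and 24. The further rows on criterion 9 are, in order:

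1. "9-1 only, 9-2 only and both 9-1 and 9-2"
2. "9-1-1 only, 9-1-2 only, 9-1-3 only, and 9-1-1 and 9-1-3, and 9-1-2 and 9-1-3"
3. "9-1-1 or 9-1-2) versus (9-1-2 and 9-1-3) versus 9-1-3 only" (an opening bracket precedes the quoted words)
4. 9-1 set against 9-2, with neither side marked as *only*
5. "9-1 only) versus (9-1 and 9-2) or (9-2 only"
6. "9-2 only) versus (9-1 and 9-2) or (9-1 only"

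The parent bullet in the same section already defines the split into 9-1 only, 9-2 only and both, and marks it for a figure.

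SAP 2.5.2 and the code in SAP 5.3.2 fit each subgroup analysis as one MMRM with visit, a single class variable for subgroup category, and their interaction. The code requests least-squares means by visit and category with confidence limits, and no differences between categories. SAP 2.5.2 says that p-values are descriptive.

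**The concern.** A row that sets groups against each other, analysed with one categorical factor, needs each patient to belong to one group. In row 3 a patient with 9-1-2 and 9-1-3 fits both the first and the second group, and the SAP does not say where that patient goes. Two programmers working from the same SAP could produce different tables. A reader could then take the figures for the first two groups as coming from different patients when they do not.

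Row 4 has a milder form of the problem, because patients who meet both 9-1 and 9-2 appear on each side. These rows separate patients who did not respond to their previous drug from patients who had difficulty taking it. Readers are likely to look at that split, since Protocol 1.2 says the study aims to enrol non-responders.

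**Working it through.** **Inputs.** The group definitions come from SAP 2.2.1.1, the rule that several conditions may be met from Protocol 4.1 and the Protocol summary, and the model from SAP 2.5.2 and 5.3.2. The SAP does not define the labels 9-1-1, 9-1-2 and 9-1-3. They are taken as the three conditions of 9-1 in listed order. The plan states no figure on this point; its sample size of 97 is not involved.

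**Step 1: row 3 as worded.** Three conditions, at least one met, give 2³ − 1 = 7 patterns.

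| Conditions met | Group 1: 9-1-1 or 9-1-2 | Group 2: 9-1-2 and 9-1-3 | Group 3: 9-1-3 only |
|---|---|---|---|
| 1 | yes | | |
| 2 | yes | | |
| 3 | | | yes |
| 1, 2 | yes | | |
| 1, 3 | yes | | |
| 2, 3 | yes | yes | |
| 1, 2, 3 | yes | yes | |

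Both patterns in group 2 are also in group 1, so group 2 is a subset of group 1. Group 3 overlaps neither.

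**Step 2: other readings.**
- *And* read as exactly those two conditions: pattern 2, 3 is still in groups 1 and 2.
- *Or* read as one but not both: pattern 2, 3 is still in groups 1 and 2, and pattern 1, 2 falls in no group.
- An unwritten *without 9-1-3* added to group 1: the overlap goes, but pattern 1, 3 falls in no group.

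None of these readings gives disjoint groups that cover all 7 patterns.

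**Step 3: the model.** One class variable holds one value per patient. To fit row 3, the programmer must choose an assignment rule, duplicate the records of shared patients, or fit separate models. Duplicates under the same identifier give two records per visit; under a new identifier they treat one patient as two independent subjects. Separate models are valid as displays, but they set group 1 beside its own subset.

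**Step 4: direction of any distortion.** Let f be the share of group 1 that is also in group 2. For simple means from separate runs, mean(G1) = f × mean(G2) + (1 − f) × mean(rest of G1). Hence mean(G1) − mean(G2) = (1 − f) × [mean(rest of G1) − mean(G2)]. Sharing patients pulls the two estimates together. The documents give no value for f, so the size cannot be stated.

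**Step 5: rows 4 to 6.** There are three patterns: 9-1 only, 9-2 only, both. Row 4 counts *both* on each side. Rows 5 and 6 place each pattern once.

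**Step 6: a disjoint version of row 3.**
- (9-1-1 or 9-1-2) without 9-1-3: patterns 1; 2; and 1, 2.
- (9-1-1 or 9-1-2) with 9-1-3: patterns 1, 3; 2, 3; and 1, 2, 3.
- 9-1-3 only: pattern 3.

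That places 3 + 3 + 1 = 7 patterns, each once. Pattern 1, 3 moves from group 1 to group 2.

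**The case against.** The best defence is that *versus* here is only a way of listing displays. The code asks for no difference between categories, and p-values are descriptive. The SAP also plans other displays that one factor cannot carry, such as "treatment regimen (e.g., overall, 1-step and 3-step titration", where the overall group contains the other two. All patients meeting 9-1 and all meeting 9-2 are valid marginal summaries, and the exclusive split is planned beside them.

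For row 4 this largely stands. What remains is a misleading label and an unreported overlap. A reader might infer that the row should be deleted, but the documents do not support that: the all-9-1 estimate describes the non-responders the study set out to enrol.

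For row 3 the defence does not succeed. No other row gives a complete disjoint version of the same grouping. Row 2 is the closest, but even with *and* read as exclusive it leaves out patients with 9-1-1 and 9-1-2, with or without 9-1-3.

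Two stronger inferences also fail. One is that group 2 will be empty: that follows only if patients are assigned to the first matching group in listed order, and the SAP sets no such rule. The other is a percentage by which a difference is diluted: this needs an assumed share of overlapping patients and a subtraction that the SAP does not request.

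**Conclusion.** Row 3 is wrong as written: its second group is contained in its first, and the specified one-factor model cannot represent it. This follows from the text and needs no assumed number. It does rest on reading the three labels as the three conditions in order. The full subset relation also needs the ordinary inclusive *or*; with an exclusive *or* the overlap is partial but remains. Row 4 is a secondary labelling point.

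The importance is minor. These are exploratory subgroup displays, and neither the primary analysis nor the sample size depends on them. Pattern counts are not patient counts: 2 of 7 patterns does not mean 2 of 7 patients, and the overlap could be small or large. A reader should not infer that the trial's main result is compromised, or that the whole subgroup list is faulty.

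**What to change.** Redefine row 3 with mutually exclusive groups. One option is the disjoint version in step 6: decline on MMSE (9-1-1 or 9-1-2) without 9-1-3, decline with 9-1-3, and 9-1-3 only. Because it moves patients who have 9-1-1 and 9-1-3 but not 9-1-2 into the second group, and the documents do not state the intended contrast, the sponsor should confirm the grouping.

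For row 4, keep the all-9-1 and all-9-2 estimates as separate displays, remove *versus*, and report how many patients are in both. Take any comparison from the planned split into 9-1 only, 9-2 only and both.

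The cost is SAP wording and reprogramming of two exploratory rows, with no new data. If the tables already exist, a footnote giving the assignment rule used and the number of shared patients would make them interpretable.
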